#### 5.2 Data Collected from the Medical Record

The following data will be obtained from the medical record and recorded in the study specific database:

- Age at registration, gender
- Prior anti-cancer therapy
- Concurrent medications from the time of informed consent through end of participation
- VEGF-TKI dose and administration
- Smoking status
- Response status (as noted by treating investigator: PD, SD, CR, PR)

#### 6.0 BLOOD SPECIMENS, ASSESSMENT OF TREG, STAT3 AND MDSC

#### 6.1 Research Blood Specimen Collection and Transfer to Processing Laboratory

One 10ml CPT tube will be collected within 7 days before start of VEGF-TKI, during week 3, and during week 13 (+/- 1 week). The pre-treatment sample may be collected on the morning of initiation of therapy, so long as the sample precedes VEGF-TKI intake. Efforts will be made to collect the sample at the time of

IRB Protocol No. 16088 Version Date: 06/12/2020

routine blood sample collection. Blood will be collected into 10 mL CPT vacuum tube, inverted slowly about 8-10 times, maintained at room temperature.

The sample will be labeled with the date, time of collection, IRB # 16088, and the participant's unique research participant number, prior to the prompt transport to the laboratory of [name] for correlative analyses.

The [name] laboratory should be notified of planned samples via email ([contact]) or other laboratory designee preferably at least a day in advance of sample collection.

# 6.2 Initial Sample Processing – Isolation of PBMCs

Processing of samples will occur at in the laboratory of [name]. The 10ml CPT tube samples will be processed within 4 hours of collection to avoid degradation of the phosphomoieties (i.e., pSTAT3) assessed in this protocol. CPT tubes will be centrifuged at 1800 x g (approximately 2800 rpm on a Sorvall RT6000 centrifuge) for 20 minutes at room temperature. After centrifugation, plasma in the CPT tubes will be gently pipetted against the gel plug to dislodge cells stuck to the top of the gel. The cell suspension will be transferred to a 50 mL conical polypropylene tube. cRPMI will be added to a total of 40 mL. A 10 mL aliquot of cell suspension for counting will be removed. The 50 mL tubes will then be centrifuged at 250 x g for seven minutes at room temperature. When centrifugation is complete, the supernatant will be aspirated. PMBCs will be either cryopreserved or used fresh.

#### 6.3 Sample Analysis

Analysis of samples for Treg, STAT3 and MDSC will occur in the laboratory of [name]. Relevant WBC subsets will be conducted through previously reported techniques. PBMCs will be immersed in a mixture of PBS, 2% FCS and 0.1% (wt/vol) sodium azide with Fc III/IIR-specific antibody to block nonspecific binding and stained the cells with different combinations of fluorochrome-coupled antibodies to CD11c, I-Ab (MHC class II), CD86, CD11b, Gr1, CD49b, CD3, CD25 or Lag-3, or with annexin V (BD Biosciences). We collected fluorescence data on FACSCalibur (Beckton Dickinson) and analyzed them using FlowJo software (Tree Star). This method has been previously published by Chalmin *et al.*

# 7.0 DIETARY INTERVENTION, STOOL SPECIMENS, MICROBIOME PROFILING

#### 7.1 Dietary Intervention

Using methods described in statistical analysis, patients will be randomized either to a probioticsupplemented group or a probiotic-restricted group for 3 months. If patients are randomized to the probiotic-supplemented group, they will be asked to purchase Activia vanilla yogurt. Patients will be asked to consume one 4 oz serving of Activia vanilla yogurt in the morning and one 4 oz serving of Activia vanilla yogurt in the evening for a total of 3 months. Patients will be cautioned not to take alternative Activia products, such as Activia Greek yogurt, Activia drinks, etc., and should not consume other flavors of Activia yogurt (i.e., fruit-containing yogurt). Patients will further be asked to be mindful of storage directions for Activia, as listed in the product label, and to further abide by expiry dates for the product. Patients enrolled on this arm should not take other yogurt or yogurt-containing foods, and should also refrain from probiotic supplements during the three month study period. Notably, methods for this randomization (i.e., recommendation of a dietary intervention without direct supply of actual food contents) replicates the format of a large prospective study published in the New England Journal of Medicine assessing the cardiac benefit of a Mediterranean diet. If patients are randomized to the probiotic-restricted group, they will be asked to not take other yogurt or yogurt-containing foods, and should also refrain from probiotic supplement during the 3 month study period. At the conclusion of the 3-month study period (or earlier if VEGF-TKIis withdrawn due to progression or toxicity or the patient is taken off this protocol

IRB Protocol No. 16088 Version Date: 06/12/2020

by patient or physician choice), patients may submit receipts to the study coordinator for reimbursement for Activia. As discussed subsequently, the dietary logs should reflect all oral intake, including dietary interventions prescribed by this study.

#### 7.2 Stool Specimen Collection

Fecal material will be collected in a 100 mL collection container by patients. A standard operating procedure (SOP) has been generated for stool collection, as outlined in Appendix A. Stool collection kit contents are listed in Appendix B. A copy of this SOP will be provided to the patient and their understanding of the SOP will be documented by the PI.

All samples will be collected by participants at home and dropped to a FedEx location on the day of sample collection and prior to that day's final delivery. Samples will be affixed with the subject's research participant number and the date on which the sample was collected. The collection container will be placed in a FedEx box that is pre-labeled with the address of [name] laboratory. The sender address will be denoted as the City of Hope Duarte campus ([name]) and will not show the subject's personal address. The sample will arrive at [name] laboratory the next day and will be stored in [name] laboratory until processing and analysis.

Samples will be collected pre-treatment, week 2, week 3, week 4, and week 13 of VEGF-TKI treatment. Participants who stop taking VEGF-TKI prior to week 13 will have a final sample collected within a week of the decision to end VEGF-TKI treatment.

In addition, participants will be requested to provide a stool sample at the earliest feasible occasion following onset of diarrhea. The specimen should be collected and dropped off to a FedEx location prior to that day's final pickup on a Monday through Thursday.

#### 7.3 Laboratory Processing and Analysis

All stool samples from subjects accrued to the study on or before the the date of this protocol will be sent to and stored in the laboratory of [name]. Stool stored in [name] laboratory will be transferred to [name] laboratory at TGen North, to the attention of [name] ([name]) for processing and final analysis. All stool samples from subjects accrued to the study after the date of this protocol will be sent directly to [name] laboratory at TGen North in Flagstaff, AZ.

#### Bacterial microbiome analysis

Total genomic DNA will be isolated from 0.25 g of feces using the PowerSoil DNA isolation kit (Mo Bio, USA). Purified DNA will be separated on a 1% agarose gel and quantified by densitometry and spectrophotometry (NanoDrop 1000; Thermo Scientific, USA). As described by Stearns *et al*, a PCR protocol will be used to amplify bacterial 16S rRNA genes from all samples. Following PCR primers including Illumina part of adapter sequences will be used to amplify V4 and V5 regions.

V4-F: ACACTCTTTCCCTACACGACGCTCTTCCGATCTGTGCCAGCMGCCGCGGTAA.

V4-R: ACACTCTTTCCCTACACGACGCTCTTCCGATCTGTGCCAGCMGCCGCGGTAA.

V5-F: ACACTCTTTCCCTACACGACGCTCTTCCGATCTGATTAGATACCCTGGTAG.

V5-R: GTGACTGGAGTTCAGACGTGTGCTCTTCCGATCTCCGTCAATTCMTTTGAGTTT.

Complete Illumina adapter and barcodes will be added by another 5 cycles of PCR to make Illumina library. After bioanalyzer and qPCR checking for QC. Multiple libraries will be mixed equally. Paired-end of sequencing (250bp or 300bp) will be performed by Illumina MiSeq V2/V3. Sequences will be clustered at

IRB Protocol No. 16088 Version Date: 06/12/2020

a variety of percent identities using USEARCHalgorithm against the closed=reference. Taxonomy will then be assigned using the RDP 2.4 classifier as described in *Smith et .al*.

Illumina MiSeq high throughput sequencing will be used to sequence the 16S rRNA gene. Libraries will be constructed for all samples by amplification of V4 or V5 region of bacterial 16S rRNA. Barcodes will be created to uniquely index and label each sample for multiplex Illumina sequencing with paired end reads. Multiple test runs will be created first to ensure the validity in 16S rRNA amplification from the fecal samples and standard QC will be performed to examine the quality of multiplex Illumina sequencing. Low-quality reads will be removed and only reads that are perfectly match the assembly will be kept for further downstream analysis.

#### Fungal microbiome analysis

DNA will be extracted from stool samples using the MagMax PowerMicrobiome extraction kit using the KingFisher Flex magnetic purification system (ThermoFisher, Waltham, MA). All DNAs will be validated for purity and integrity by agarose gel electrophoresis, and fungal load will be quantitated using the FungiQuant TaqMan assay before proceeding to sequencing. DNAs will be subjected to internally transcribed spacer gene sequencing using the )ITS4-Fun AGCCTCCGCTTATTGATATGCTTAART and 5.8S-Fun AACTTTYRRCAAYGGATCWCT primers with dual-indexed bar codes as described by Kozich et al.  A DNA mock community that contains two fungal species will be sequenced as a positive control (Zymo, D6306) as will an extraction blank as a negative control. Libraries will be quantitated using KAPA Library Quantification Kit (KAPA Biosystems), normalized and pooled then sequenced on the Illumina MiSeq instrument using the v2 kit (2 x250 bp) targeting 20,000 reads per sample.

Demultiplexed ITS reads will be processed and clustered into operational taxonomic units (OTUs) using QIIME2. Demultiplexed reads will be denoised using dada2 then clustered into OTUs using q2-dbotu. Taxonomic classification will be performed using feature-classifier classify-sklearn. Various QIIME2 plugins will be used to build a phylogenetic tree (phylogeny), calculate alpha diversity within samples (diversity plugin) and beta diversity between samples (diversity plugin). We have found that simple alpha diversity calculations, such as inverse Simpson diversity, Shannon and Chao estimates, and examination of the dominant genera in each sample provides a good first impression of the composition of the sample. We will use several different types of distance methods (Bray Curtis, UniFrac) to examine and compare the community distribution of the samples. These data will be examined by multidimensional scaling or principal components analysis and heatmaps will be created using hclust2.

Whole metagenome sequencing provides a complete picture of the taxonomic composition of a microbiome than does 16S rRNA gene or ITS sequencing and also permits predictions of microbiome function, which we can tie to metabolic and proteomic results. Metagenomics also has been used for the discovery of clinical biomarkers and will allow us to identify antibiotic resistance genes. Metagenomic DNA will be sequenced on the Illumina NextSeq platform to a depth of 2 Gb/sample.  Human reads will be identified by mapping them to the human genome GRCh38.p7 using BowTie2 and they will be removed. Demultiplexed reads will be quality trimmed using Trimmomatic to remove adapters and low-quality bases and reads.  Trimmed metagenomic reads will be taxonomically profiled using MetaPhlAn 2.0. Functional profiling of the metagenomes will be performed using HUMAnN2, which annotates open reading frames (ORFs) and generates gene family abundances, metabolic pathway coverage and abundances. Antimicrobial resistance genes will be identified by mapping to a curated version of the Resfams database. Resistance genes of interest will be verified by targeted amplicon sequencing. 

IRB Protocol No. 16088 Version Date: 06/12/2020

#### 8.0 STATISTICAL CONSIDERATIONS

### 8.1 Study Design and Statistical Analysis

Primary Objective:

Compare the change from baseline *Bifidobacterium spp.* between the Activia group and the group without Activia.

The primary measurement is the abundance of Bifidobacterium spp. in stool since probiotic formulations including Bifidobacterium spp. have been noted to improve acute diarrhea in a multitude of settings and mRCC patients in our pilot study have very low abundance of Bifidobacterium spp. The objective is to determine whether the levels of Bifidobacterium spp. increase in patients getting Activia™, and compare to a control group. Operational taxonomic units (OTUs) for bacterial will be identified by QIIME and the relative abundance will be estimated as the percentage of reads belong to certain OUT. T-test or mann-whitney test will be used to test the difference in change from baseline in relative abundance for Bifidobacterium spp. between patients with or without Activia™ added to the diet. If the data appear symmetrical and the t-test is used, with 20 patients enrolled and 10 in each group, assuming equal variance in each group, using one-sided t-test at type I error of 0.05, we will have 80% power to detect a larger change in average abundance of Bifidobacterium spp in patients receiving Activia™ than those who are not randomized to take Activia™. If abundance and change is too low in the non-Activia™ arm to employ the t-test, we will employ the Mann-Whitney test. A sample size of 10 in each group will have 85% power to detect a probability of 85% that an observation in the change in Bifidobacterium spp abundance in the Activia ™ arm is larger than an observation in the change in the non-Activia ™ arm using a Wilcoxon (Mann-Whitney) rank-sum test with a 0.050 one-sided significance level.

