# COH IRB 12096: A Pilot Study

The current team of investigators embarked on a project sponsored by the COH Cancer Center Core Grant. We collected random stool samples from a cohort of 23 patients with mRCC while receiving VEGF-directed therapies. Ultimately, 20 patients provided satisfactory samples for evaluation. Amongst these patients, the majority were treated with sunitinib or pazopanib. 16S rRNA profiling using the methods described herein was used to characterize the stool bacterial flora of these patients. Patients receiving VEGF-TKIs with mRCC appeared to have less relative abundance of Bifidobacterium spp as compared to previous reports based on healthy subjects. Patients also had higher levels of Bacteroides spp and lower levels of Prevotella spp were found in patients with diarrhea.

We interpret the results of COH IRB 12096 cautiously, as there are several caveats to this work:

- 1. The sample size is small,
- 2. There was heterogeneity of treatments rendered
- 3. Stool collections were done at random time points
- 4. There was no control of dietary factors

Despite the aforementioned limitations, COH IRB 12096 established the feasibility of stool collections and subsequent bacteriomic analysis and suggested the possibility that the propensity for the diarrhea observed could be due to the low abundance of Bifidobacterium spp observed in this patient population and that supplementing with Bifidobacterium would change the flora and also change the relative abundance of Bacteroides. An SOP for stool collection and analysis was developed that will be implemented in the current study.

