Several stool collections will be performed. Stool samples will be collected prior to initiating VEGF-TKI treatment, one week after initiating therapy, two weeks after initiating therapy, three weeks after initiating therapy (i.e. after the first week off of therapy), three months (13 weeks) into VEGF-TKI therapy, and at the onset of diarrhea. A stool specimen at the onset of diarrhea would reflect changes in the bacteriome that could potentially drive onset of this symptom. Compliance with stool submission has not been an issue in our pilot study (IRB 12096). All stool samples will be collected by the participant at home and sent via overnight shipping to the laboratory at City of Hope. Participants will receive training on the sample collection process. Participants will also be asked to complete a diet log and stool frequency log that uses the CTCAE v4.0 definitions of diarrhea:

IRB Protocol No. 16088 Version Date: 06/12/2020

- Grade 1: Increase of <4 stools per day over baseline; mild increase in ostomy output compared to baseline
- Grade 2: Increase of 4 6 stools per day over baseline; moderate increase in ostomy output compared to baseline
- Grade 3: Increase of >=7 stools per day over baseline; incontinence; hospitalization indicated; severe increase in ostomy output compared to baseline; limiting self care ADL
- Grade 4: Life-threatening consequences; urgent intervention indicated
- Grade 5: Death

For purposes of the current study, we are interested in characterizing the incurrence of all grade diarrhea (e.g., grade 1-5 toxicity); however, the grade of diarrhea incurred will be specified.

From the serial stool samples, *Bifidobacterium spp*. levels and stool bacteriomic profile over time will be assessed and associations will be examined between patients who experience diarrhea and those who do not.

To explore potential confounding factors or associations of interest between the bacteriomic profile and the presence of diarrhea, data collection will include: intake of yogurt, general description of daily diet, prior anti-cancer therapies, concomitant medications during the study period, and response to VEGF-TKIs. These data will be collected from the participant's medical record or from the participant's daily log.

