#### 4.0 STUDY ACTIVITY TABLE

# 4.1 Study Activity Table

	Screeninga Pre-tx		VEGF-TKI treatment b				
	Screening a	FIE-LX	Wk 1	Wk 2	Wk3	Wk 4	Wk 13
Informed consent C	Х						
Eligibility review d	Х						
Registration e	Х						
Participant orientation f		xf					
Research blood collection g		χg			χg		χg
Planned stool specimensh		χi		χj	χj	χj	χj
Stool specimen at onset of diarrheah			Xk				
Study log review/collection					χl		χl
Data collection m			Х		Х		Х
Dietary intervention n		χn		χn	χn	χn	χn
PHQ-9 and GAD-7 °		X					X

- a. Screening procedures are to occur prior to research sample collection with the following caveat: If the sample is collected on the same day as completion of eligibility review, the informed consent and eligibility review must precede sample collection; registration must occur that very day but may be before or after sample collection.
- b. Participants who end vascular endothelial growth factor tyrosine kinase inhibitor (VEGF-TKI) treatment prior to Week 13 will jump to the 'Week 13' assessments which will be performed within 1 week of the decision to end VEGF-TKI treatment.
- c. Informed consent to occur before any study specific screening procedures.
- d. Inclusion/exclusion criteria are found in Section 3.2. Source documentation providing investigator's confirmation that patient has met all eligibility criteria must be available prior to registration.
- e. Registration into MIDAS.
- f. Participants will receive training on completion of the diet log, stool frequency log, and stool specimen collection SOP by the clinician investigator. This education will be noted in the medical record.

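### Section 8.1 names no primary visit among four post-baseline stools and picks the test after seeing the data; the stated 5% error holds only if both are fixed in advance

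*Combined protocol and SAP*

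**What the plan says.** Section 8.1 (Primary Objective) sets one between-arm comparison: "T-test or mann-whitney test will be used to test the difference in change from baseline in relative abundance for Bifidobacterium spp". Both versions of the test are one-sided at 0.05 with 10 per arm. No visit, average over visits, repeated-measures model or multiplicity rule is given.

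The choice of test depends on the data. One branch opens "If the data appear symmetrical and the t-test is used". The other applies when abundance and change are too low in the control "arm to employ the t-test, we will employ the Mann-Whitney test". Neither condition has a threshold. The t-test branch claims 80% power without an effect size. The Mann-Whitney branch claims 85% power for a probability of 0.85 that a change in the Activia arm exceeds one in the control arm.

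Section 7.2 gives the stools: "Samples will be collected pre-treatment, week 2, week 3, week 4, and week 13 of VEGF-TKI treatment". Footnote j of the Section 4.1 table lists the same four post-baseline weeks. Patients who stop VEGF-TKI early "will have a final sample collected within a week of the decision to end VEGF-TKI treatment", and footnote b of the table says they "will jump to the 'Week 13' assessments which will be performed within 1 week of the decision to end VEGF-TKI treatment".

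Three places lean towards Week 13. Section 2.1 (Psychosocial aspects) times the second questionnaire at Week 13 to fit the stool assessments, Section 2.2 describes a three-month intervention, and footnote b uses the Week 13 label for early stoppers. None of them makes Week 13 the primary visit. Section 2.2 also says of the serial samples that Bifidobacterium "levels and stool bacteriomic profile over time will be assessed".

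**The concern.** The plan has one formal test but four possible outcomes for it. All four results will be on hand at the analysis, and nothing written says which one counts. A one-sided 5% error rate describes a single comparison chosen before the data are seen.

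The visits may also not measure the same thing. Footnote n of Section 4.1 starts the yogurt in Week 2, and footnote j allows the Week 2 stool on any Monday to Thursday of that week, so that stool may reflect little exposure. The schema footnote instead has yogurt taken throughout the study. Without a named visit, the effect being estimated is undefined even if nobody selects among results.

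Leaving the test open until the data are inspected is a second loose end. So is a power claim with no effect size, because the reader cannot tell what 20 patients are able to show.

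**Working it through.** **Inputs from the documents.** 10 per arm, one-sided 0.05, four post-baseline visits (Sections 7.2, 8.1). Pilot yield: stool was collected from 23 patients and "Ultimately, 20 patients provided satisfactory samples for evaluation" (Section 2.1).

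**Inputs assumed.** The documents give no correlation between the visits' changes, so I use 0 to 0.9 with 0.5 as the centre. Four changes that share one baseline have correlation 0.5 if variances are equal and visits exchangeable.

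**1. The plan's own power figure.** Noether's formula for Mann-Whitney is power = Φ(√(3N)(p − 0.5) − 1.645). With N = 20 and p = 0.85: √60 × 0.35 = 2.711; 2.711 − 1.645 = 1.066; Φ(1.066) = 85.7%. The stated 85% reproduces, for one test.

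**2. What the 80% t-test power means.** With 18 degrees of freedom, critical value 1.734 and noncentrality d√(10/2), 80% power needs d = 1.156, about 1.16 SD of the change. For normal data this is P(X > Y) = Φ(1.156/√2) = 0.79. The Mann-Whitney statement uses the larger 0.85, which is 1.47 SD if normal.

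**3. Error rate if the most favourable of four visits is reported.** At zero correlation, 1 − 0.95⁴ = 18.5%. Simulated t-tests with 10 per arm and equally correlated normal changes:

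| Correlation | One fixed visit | Best of 4 | Best of 3 (no Week 2) |
|---|---|---|---|
| 0 | 5% | 18-19% | 14% |
| 0.5 | 5% | 14.5-14.7% | 12% |
| 0.9 | 5% | 9% | 8% |

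The exact Mann-Whitney test alone gives 13.6% for best of four at 0.5.

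**4. Contribution of the test choice.** At one visit, reading the rule as Mann-Whitney when |skewness| > 1 (an assumed threshold) gives 4.7-5.2%. Keeping the better of the two p-values gives 5.6-6.0%. Most of the possible inflation therefore comes from the visit. Free choice of both visit and test gives 16.2% at 0.5 and 20.2% at 0. Counting the diarrhea-onset stool as a fifth look (t-test) gives 16.6% and 22.6%.

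**5. Baseline adjustment.** Let rho be the correlation between baseline and follow-up abundance. With equal SDs, the residual variance of ANCOVA relative to the change score is (1 − rho²)/(2(1 − rho)) = (1 + rho)/2, or 0.65, 0.75, 0.85 and 0.95 at rho 0.3, 0.5, 0.7 and 0.9. Where the change-score t-test has 80% power, simulated ANCOVA power is 91%, 87%, 83% and 79-80%. In the unfavourable case, baseline SD / follow-up SD = rho, the regression slope is exactly 1. The change score is then already optimal, and ANCOVA has 77-78%.

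**6. Lost stools.** A change needs two usable stools. At the pilot's rate, and if failures are independent, 20 × (20/23)² = 15.1, so about 15 of 20 patients would be evaluable. With 8 v 7, t-test power at 1.16 SD is about 68%.

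**The case against.** The strongest reply is that the inflation is hypothetical. Section 8.1 describes one comparison, and no section says that each visit will be tested between arms or that the best will be reported. The three-month intervention, the early-stop rule and the questionnaire timing all point to Week 13. This stands. A reader might infer that the trial runs at a 15% error rate, or that the plan intends to search the visits; the documents support neither. What they support is that Week 13 is implied and not stated.

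A reader might also take 15%, or 19%, as a ceiling. It is not: step 4 shows that other freedoms in 8.1 can take it higher. Nor is the range firmly anchored. A correlation near 0 would need a baseline SD well below the later SDs, because the changes share one baseline.

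Applying the pilot's 20 of 23 once per patient suggests 17 evaluable patients. That overlooks the second stool that a change requires. The pilot's stools were also taken at random time points, so even 15 is only indicative.

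ANCOVA is a preference. The change score itself adds no inflation, and a fixed change-score test would protect the error rate equally well. Analysing early-stop samples as Week 13 mixes lengths of exposure, which the plan should acknowledge. The schema figure is missing from the text I had, but its footnotes name no primary visit.

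**Conclusion.** The point holds as a cheap improvement. Section 8.1 leaves the primary visit unnamed and lets the data pick the test, so its 5% error rate is not guaranteed as written. If the most favourable visit were reported, the t-test error would be about 15%, with a range of 9% to 18-19% over assumed correlations of 0.9 to 0. This is conditional on a practice that the plan does not describe, and it covers visit choice only. The test rule adds little at a single visit. The 80% t-test power corresponds to 1.16 SD of the change with all 20 pairs usable. It falls to about 68% if 15 pairs are usable, which assumes the pilot's rate and independent failures. The gain from baseline adjustment depends on a rho and an SD ratio that the documents do not give. Confidence is medium.

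**What to change.** In Section 8.1:

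1. Name Week 13 as the primary visit, which fits the three-month intervention. State that the early-stop final sample of Section 7.2 and footnote b of Section 4.1 is analysed in its place, and how a patient with no usable stool at baseline or at that visit is handled. Label Weeks 2-4 supportive.
2. Replace the data-dependent choice with one test on one scale, fixed before data are seen. Preferably use ANCOVA on arm and baseline abundance, on the log scale if skew is expected, since the baseline stool is already collected. A fixed change-score test is an acceptable alternative.
3. State that the 80% t-test power applies to a difference of 1.16 SD of the change with all 20 pairs usable.

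The schema footnote and the Section 4.1 table with its footnote n must be reconciled on when the yogurt starts, because this determines what the early stools measure.

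Cost: a few sentences, with no extra patient, sample or assay. ANCOVA uses one degree of freedom and loses 2-3 points of power if baseline SD / follow-up SD equals rho.

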#### 8.2 Sample Size and Projected Accrual Rate and Study Duration

Twenty participants will be metastatic renal cell carcinoma will enroll to the study. Enrollment is expected to be completed in 3 years, and the study is expected to be completed in 3.5 years.

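### Does the 80% t-test power in Section 8.1 fail because no effect size is given with it?

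*Combined protocol and SAP*

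**What the plan says.** The Primary Objective part of Section 8.1 compares the change from baseline in relative abundance of Bifidobacterium between the Activia and non-Activia groups, by t-test or Mann-Whitney test.

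The t-test applies on a condition: "If the data appear symmetrical and the t-test is used". Its power is computed "with 20 patients enrolled and 10 in each group, assuming equal variance in each group", "using one-sided t-test at type I error of 0.05", and the claim is that "we will have 80% power to detect a larger change in average abundance of Bifidobacterium spp" with Activia than without. No difference, SD or standardized effect accompanies the 80%.

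The Mann-Whitney test is the fallback when abundance and change in the non-Activia arm are too low for a t-test. Its power sentence does name an effect: "A sample size of 10 in each group will have 85% power to detect a probability of 85"%, meaning the probability that a change in the Activia arm exceeds one in the other arm, again one-sided at 0.05.

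Section 8.2 gives enrolment as 20 and adds no effect size. The pilot description in Section 2.1 reports no mean or SD of Bifidobacterium abundance.

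**The concern.** Power is defined only at a stated effect. Taken literally, 80% power for any larger change is untrue: small increases would usually be missed. The other two power statements in Section 8.1 (Mann-Whitney, and Fisher's exact test for diarrhea at 0.200 against 0.800) each name their effect. The one for the primary t-test does not.

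Two further points add to the impression of a fault. The 80% and 85% stand side by side, so a quick reader might think that falling back to the rank test gains power, although the two figures are quoted at different effects. The 80% also counts all 20 enrolled patients as evaluable, with no allowance for loss.

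What would be at stake is the reading of a null result. If the 80% were taken at face value, a non-significant primary comparison could be mistaken for evidence against any increase in Bifidobacterium.

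**Working it through.** **Inputs, all from Section 8.1.** n = 10 per group; one-sided alpha 0.05; equal variances; t-test power 80%; Mann-Whitney power 85% at P = 0.85. No SD of change is given anywhere, so effects are in units of that SD, written d.

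**1. The Mann-Whitney figure.** Noether's formula with N = 20 and equal allocation is power = Φ(√(12 × N × 0.25) × (P − 0.5) − z₀.₉₅). This gives √60 × 0.35 − 1.645 = 2.711 − 1.645 = 1.066, and Φ(1.066) = 0.857. The stated 85% reproduces. Simulating the exact rank-sum test under a normal shift gives about 91%, so the stated figure is, if anything, conservative.

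**2. The effect behind the t-test's 80%.** Power is the probability that a non-central t with 18 degrees of freedom and non-centrality d × √(10 × 10/20) = d√5 exceeds t₀.₉₅ = 1.734. Setting this to 0.80 and solving gives d = 1.156. There is one solution, because power rises steadily with d.

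| True difference (SD of change) | t-test power, 10 + 10 |
|---|---|
| 0.5 | 28% |
| 0.75 | 49% |
| 1.0 | 69% |
| 1.156 | 80% |
| 1.466 | 93% |

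The smallest observed difference that reaches significance is 1.734 × √(2/10) = 0.775 SD.

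**3. Are the 80% and 85% in conflict?** Under normal data with equal variances, P = 0.85 converts to d = √2 × 1.0364 = 1.466. The two figures are therefore quoted at different effects, 1.156 and 1.466 SD. Each is right at its own effect, and the text does not compare them.

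Which test has more power at a common effect depends on the distribution:

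- Normal data, d = 1.156: t-test 80%, exact Mann-Whitney about 76%.
- Exponential data with a shift of 1.156 SD (an assumed shape, simulated with 10 + 10): t-test 81%, Mann-Whitney 88%.
- Exponential data with a shift of 1.466 SD: t-test 92%, Mann-Whitney 95%.

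The plan falls back to Mann-Whitney when abundance and change are too low for a t-test. The normal case is not the one in which it would do so.

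**4. Loss of patients.** At d = 1.156, t-test power is 78% with 19 evaluable (10 + 9), 73% with 17 (9 + 8) and 68% with 15 (8 + 7). These counts are illustrations; the documents give no expected loss. Footnote b in Section 4.1, and Section 7.2, require a final stool from patients who stop VEGF-TKI early, and stools are also planned at Weeks 2, 3 and 4. Early stopping therefore need not cost a post-baseline value.

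**5. Could the plan state the effect in abundance units?** That needs an SD of change from a pre-treatment baseline. The pilot describes its material thus: "We collected random stool samples from a cohort of 23 patients with mRCC while receiving VEGF-directed therapies". Those stools were taken at random times during treatment, so the pilot as described has no pre-treatment baseline from which to form such a change. No other source is offered.

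**The case for a change.** The strongest case for a change is that this is the primary comparison, that the sentence is complete rather than garbled, and that neighbouring power statements do name their effects. A small trial makes the detectable effect more important: a true increase of 1.0 SD would be missed 31% of the time, and one of 0.5 SD 72% of the time. Without an SD, nobody can judge whether yogurt could plausibly produce 1.16 SD. One clause would cost almost nothing.

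The omission and these figures stand. What does not stand is that the 80% cannot be verified. The other inputs determine the standardized effect, and any statistician would recover it in a line. The missing conversion to abundance units is real, but no amendment could supply it from the documents. The claim that the fallback loses power holds under normality and reverses in the skewed example, so it is no ground for rewording the Mann-Whitney sentence. The feared misreading of a null result is not invited by anything in the plan; a report with the estimated difference and its confidence interval would guard against it better than a reworded power sentence.

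**Conclusion.** The concern does not call for a change. The power sentence leaves out its effect size, but nothing stated is wrong: 80% is consistent with 10 per group and one-sided 0.05 at a difference of about 1.16 SD of the change, and 85% is right at P = 0.85. Adding the number would leave the tests, sample size, visits and results as they are, so there is a small gain in clarity and none in inference.

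The 1.16 SD rests on normal changes, equal variances and 10 evaluable patients per group. It rises to 1.23 SD with 9 per group and 1.31 SD with 8. The 1.47 SD equivalent of P = 0.85 also assumes normality. Readers of the eventual result should keep in mind that the trial can reliably detect only a large shift. Which post-baseline stool defines the change, and which patients are analysed, are separate questions that this point does not settle.
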